Sources of materials: Medical information data will be collected from the participant and, after written authorization for the disclosure of protected health information, from participants' medical records. Blood and urine samples will be collected to measure HbA1c, glucose, insulin, lipids, creatinine, ketones, and test for pregnancy. Blood pressure, height, weight, waist circumference and other physical measurements will be obtained.

Potential Risks: Risks associated with venipuncture, the diet intervention, CGM insertion, and collection of confidential medical information are the main risks associated with this study. There is a small risk of bruising and a rare chance of local infection associated with standard venipuncture to collect blood samples. The risks of wearing the CGM are minimal. There is a very low risk for local infection at the skin site where the sensor is inserted into the skin. Possible symptoms associated with the CGM sensor application or the adhesive used to keep the sensor in place include skin irritation or redness, skin inflammation, pain or discomfort, bleeding, bruising, swelling, skin rash, itching, scarring or skin discoloration, or allergic reactions to the sensor needle or adhesives. Sensors may fracture *in situ* on rare occasions. The dietary intervention has minimal risks. Reduced carbohydrate consumption may lead to adverse effects, including constipation, halitosis, fatigue, headache, thirst, polyuria, and nausea. At RZ, 3-, and 6-month visits, we will administer *symptom questionnaires*, which will consist of a checklist to identify participant complaints. Adverse effects of the low-carbohydrate diet will be assessed at counseling sessions. Severe adverse events will be promptly reported to the DSMB. Management of adverse effects will be based on the protection and safety of the participant. If severe adverse effects are reported by a participant, carbohydrate intake will be examined and altered in order to mitigate the adverse effect. In any extreme cases, participants will be instructed to stop the intervention. Furthermore, there is a potential risk of unauthorized disclosure of medical information. This risk will be minimized by using a strict protocol for data processing and by the appropriate training of all study personnel. Protection against risks is described in more detail below.

16.A.2. Adequacy of protection against risks

Recruitment and Informed Consent: The proposed study will be conducted following strict guidelines for the protection of the rights of human volunteers. The informed consent document will be signed by all participants at the screening/baseline visit. The informed consent form will be developed in the first year of the study and approved by the IRB. The consent form will clearly state the purpose, eligibility criteria, and protocol of the study, the potential benefits and risks of participation, and the subject's right to refuse to participate or withdraw. Prior to signing the informed consent, research staff will review the details of the consent form orally with the participant, and answer any questions that the participant has concerning participation in the study. In the case of potential participants with low or no literacy, the informed consent form will be read to the participant in its entirety and any questions will be answered prior to the participant signing or marking the form. Specifically, the following must be accomplished during the informed consent process:

- The participant must be informed that participation in the study is **voluntary** and that refusal to participate will involve no penalty or loss of benefits.
- The participant must be informed of the **purpose** of the study and that it involves **research**.
- The participant must be informed of any **alternative procedures**, if applicable.

- The participant must be informed of any reasonably foreseeable **risks**.
- The participant must be informed of any **benefits** from the research.
- An outline of safeguards to protect participant **confidentiality** will be included, as well as an indication of the participant's right to withdraw without penalty. This should be balanced with a discussion of the effect that withdrawals will have on the study, and the responsibility a participant has, within limits, to continue in the study if he or she decides to enroll.
- The participant must be informed of his or her right to have **questions answered** at any time and **whom to contact** for answers or in the event of research-related injury.
- The participant must be informed as to whether or not **compensation** is offered for participation in the study and/or in the event of a medical injury.
- The participant must be informed that he/she will be notified of any significant **changes** in the protocol that might affect their willingness to continue in the study.

Written authorization for the disclosure of protected health information will be obtained during the consent process on a separate form (HIPPA authorization), if applicable.

Protection against Risk: The protocol and informed consent will be approved by the Institutional Review Boards at Tulane University Health Sciences Center and any other participating institution for recruitment. The study participants will be given contact information for the Study Coordinator and Study PI to answer questions or to report complaints. Patients can withdraw from the study at any time without any effect on their medical care. Standard techniques will be used by trained, certified phlebotomists or study nurses for blood sample collection at the study clinics where emergency medical equipment is available. Confidentiality of all data collected during the study will be maintained through the use of unique, encrypted study identification (ID numbers, rather than patient names, in the study database). These encrypted ID numbers will not be mathematical derivation of the subject's medical record number or any other patient identifier. No information will be disclosed in an individually identifiable form in any type of presentation or publication. There will be password-required access to the computerized file linking the study numbers to patient identifiers at the study clinics. Password-access will be restricted to pertinent research staff only. All study data will be kept in locked file cabinets in locked rooms, accessible only by study staff with permission. All data transmissions will use HIPPA-compliant password protected system and will be secured through a virtual private network.

16.A.3. Potential benefits of the proposed research to human subjects and others

Study participants may have improved glycemic outcomes, blood pressure, lipid levels, may lose weight and reduce waist circumference, and may have improvement in other risk factors for CVD and development and progression of T2D. Participants will receive multiple blood pressure, weight, waist circumference, and blood tests. If vital signs or lab values are clinically abnormal, participants will be referred to their primary care physician, or if they do not have a primary care physician, one will be assigned through the Tulane University Community Health Center, which is a part of the core clinical facilities. At the end of the study, we will provide the participants' primary care physician with a copy of all the blood pressure, weight, laboratory results, and (if applicable) CGM results.

16.A.4. Importance of knowledge to be gained

Information from this study may contribute to reducing the onset of T2D and the burden of T2D and cardiovascular disease in Louisiana and the general US population. The study has

potential for public health impact; results from this study may provide evidence in support of promoting alternative dietary styles (than the most commonly used low-fat diet) among individuals with high T2D risk or with T2D.

16.A.5. Remuneration

For screening visit 2, the two follow-up visits, and the final visits, participants will receive \$40 gift cards for use at food stores or retailers (after completing each study visit), for a maximum of \$120 over the study period. Participants who return a stool sample will receive \$25 gift cards for each stool sample that they return, for a total of \$75 for three stool samples. For the CGM 6-month study, participants will receive \$25 gift cards for returning the CGM, for a maximum of \$25. Participants will also receive free parking for each intervention and study visit.

16.B. Data safety and monitoring plan

A DSMB, which consists of 3 experts who are not otherwise affiliated with the COBRE program, has been formed. Study investigators for this study will prepare accurate and timely data tables and reports for the DSMB meetings. The members of the DSMB will serve in an individual capacity and provide their expertise and recommendations. The primary responsibilities of the DSMB are: 1) periodically review and evaluate the accumulated study data for participant safety, study conduct and progress, and, when appropriate, efficacy, and 2) make recommendations to the NIH concerning the continuation, modification, or termination of the trial. The DSMB considers study-specific data, as well as relevant background knowledge, about the disease, test agent, and patient population under study.

The DSMB is responsible for defining its deliberative processes, including event triggers that would call for an unscheduled review, stopping guidelines, unmasking (unblinding) and voting procedures prior to initiating any data review. The DSMB is also responsible for maintaining the confidentiality of its internal discussions and activities, as well as the contents of reports provided to it.

The DSMB will review each protocol for any major concerns prior to implementation. During the trial, the DSMB should review cumulative study data to evaluate safety, study conduct, and scientific validity and integrity of the trial. As part of this responsibility, DSMB members must be satisfied that the timeliness, completeness, and accuracy of the data submitted to them for review are sufficient for evaluation of the safety and welfare of study participants. The DSMB should also assess the performance of overall study operations and any other relevant issues, as necessary.

Items reviewed by the DSMB include:

- Interim/cumulative data for evidence of study-related adverse events;
- Interim/cumulative data for evidence of efficacy according to pre-established statistical guidelines, if appropriate;
- Data quality, completeness, and timeliness;
- Adequacy of compliance with goals for recruitment and retention, including those related to the participation of women and minorities;
- Adherence to the protocol;
- Factors that might affect the study outcome or compromise the confidentiality of the trial data (such as protocol violations, unmasking, etc.); and,
- Factors external to the study, such as scientific or therapeutic developments, that may impact participant safety or the ethics of the study.

The DSMB will conclude each review with their recommendations to the COBRE program and NIH/NIGMS as to whether the study should continue without change or be modified or terminated. Recommendations regarding modification of the design and conduct of the study could include:

- Modifications of the study protocol based upon review of the safety data;
- Suspension or early termination of the study or of one or more study arms because of serious concerns about subjects' safety, inadequate performance or rate of enrollment;
- Suspension or early termination of the study or of one or more study arms because study objectives have not been obtained according to pre-established statistical guidelines; and,
- Corrective actions regarding a study when the performance appears unsatisfactory or suspicious.

Confidentiality must always be maintained during all phases of DSMB review and deliberation. Usually, only voting members of the DSMB should have access to interim analyses of outcome data by treatment group. Exceptions may be made when the DSMB deems it appropriate. The reason and to whom the exceptions for access to interim analyses is granted will be documented in the Closed Session Report. DSMB members must maintain strict confidentiality concerning all privileged trial results ever provided to them. The DSMB should review data only by masked study group (such as X vs. Y rather than experimental vs. control) unless or until the DSMB determines that the identities of the groups are necessary for their decision-making. Whenever masked data are presented to the DSMB, the key to the group coding must be available for immediate unmasking.

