Our *long-term goal* is to develop and implement dietary intervention(s) that reduce risk of T2D. The *overall goal of this randomized controlled trial is to study the effect of a behavioral intervention promoting a low-carbohydrate/high-unsaturated fat and high-protein dietary pattern (initial target <40 g digestible carbohydrates, final target <60 g digestible carbohydrates) compared with a usual diet on metabolic risk factors among individuals with prediabetes or early-stage untreated diabetes (HbA1c 6.0–6.9%).* Specifically, we will test the following hypotheses:

Primary hypothesis: Compared with usual diet, over a 6-month period, a healthy low-carbohydrate/high unsaturated fat and high-protein dietary pattern will lead to a larger decrease of HbA1c, by at least 0.15%.

Secondary hypothesis: Over a 6-month period, a healthy low-carbohydrate/high-unsaturated fat and high-protein dietary pattern will lead to larger improvements in the following major secondary outcomes: fasting glucose, systolic blood pressure (BP), total-to-HDL-cholesterol ratio, and body weight.

Exploratory outcomes: We will also study the effect of the intervention on the 6-month change in: insulin and homeostasis model assessment of insulin resistance (HOMA-IR); diastolic BP; waist circumference; and estimated CVD risk.

To achieve these study aims, we will recruit 150 adults with prediabetes or untreated diabetes (HbA1c 6.0–6.9%) in the Greater New Orleans, LA area. Using a stratified, blocked randomization scheme, participants will be assigned to either a behavioral modification intervention aimed at promoting a healthy low-carbohydrate dietary pattern or to usual diet. The intervention group will have an intensive phase for 3 months, followed by a maintenance phase in months 4 through 6. The primary outcome will be difference between the active intervention and control groups in the change in HbA1c from baseline to 6 months of follow-up. We expect 80% power to detect a difference of at least 0.15% in change of HbA1c. Changes in other metabolic risk factors will be studied concurrently. Metabolic risk factors will be assessed at baseline, 3 months, and 6 months of follow-up.

There is much interest regarding dietary approaches to prevent T2D and its complications. The results from this study will help to determine whether, compared with usual diet, a behavioral intervention aimed at promoting a healthy low-carbohydrate dietary pattern improves metabolic risk factors.

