Trial personnel will all be required to participate in a training session before the start of any trial procedures or measurements. Training will include particular attention to core trial elements, such as recruitment, retention, intervention, completeness and quality of data acquisition (e.g., blinding procedures for the data collectors), and data entry. Separately, intervention staff will meet and receive detailed instruction on trial approaches to group and individual behavior change counseling and procedures that ensure data collectors are blinded to treatment assignment. Throughout the trial, periodic re-training/certification sessions will be conducted to ensure all trial-related procedures are being applied in a standard manner. Investigators will also monitor all aspects of study performance to ensure study goal achievement, timeliness and completeness of study visits, completeness and quality of data collection, intervention adherence, and adequacy of the procedures separating data collection from intervention. Study staff and investigators will pay particularly careful attention to the quality of all laboratory measurements, particularly key exposure, outcome, and intervention monitoring variables.

12. Sample Size and Statistical Power

The primary outcome will be the difference in the change of HbA1c between the intervention and usual diet groups from baseline to 6 months of follow-up. Preliminary data from ADEPT suggests that the SD of the 6-month change in HbA1c is 0.28%, with preliminary 6-month follow-up >90%. Based on an estimated standard deviation of change in HbA1c of 0.35% and 95% follow-up, we would need 142 participants to have 80% power to detect a difference in the change in HbA1c from baseline to 6 months of 0.17% between the intervention and usual diet groups. Assuming 95% follow-up, we would need 150 total participants.

In a follow-up analysis of the DPP, a 0.15% decrement in HbA1c at 6 months was associated with a 16% lower risk of incident T2D, adjusting for treatment arm, age, sex, race/ethnicity, household income, and baseline HbA1c.¹¹⁶ In a pooled analysis from the Atherosclerosis Risk in Communities and Framingham Heart Studies, a 0.15% higher HbA1c was associated with an 16% higher risk of T2D over 20 years, a 30% higher risk over 8 years, and a 13% higher risk after 8 years, after adjusting for age, sex, fasting glucose, triglycerides,

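### The Overview claims 80% power for a 0.15% HbA1c difference, but the protocol's own SD and sample size give about 72%; the 80% belongs to 0.17%

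*Combined protocol and SAP*

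**What the plan says.** The Overview (Section 1) gives the primary hypothesis as an intervention that "will lead to a larger decrease of HbA1c, by at least 0.15" per cent over 6 months. For a trial of 150 adults it then states: "We expect 80% power to detect a difference of at least 0.15% in change of HbA1c". It names no SD.

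Section 12 gives the calculation: "Based on an estimated standard deviation of change in HbA1c of 0.35% and 95% follow-up, we would need 142 participants to have 80% power". The effect size it attaches to that power is 0.17%, not 0.15%. The section adds: "Assuming 95% follow-up, we would need 150 total participants". Table 5 repeats the pair SD 0.35 and detectable difference 0.17, and the text above it specifies unpaired t-tests, 80% power, two-sided alpha 0.05 and 142 of 150 participants followed.

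Section 12 also reports a smaller SD from the trial's own early data: "Preliminary data from ADEPT suggests that the SD of the 6-month change in HbA1c is 0.28%, with preliminary 6-month follow-up >90" per cent. The calculation does not use it.

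The supporting evidence in Section 12 (associations with incident diabetes and coronary disease, and the 6-month lifestyle effect in an earlier prevention trial) is all expressed per 0.15% HbA1c. Section 13.B.2 tests whether the reduction is greater in the intervention group, by linear regression on the 6-month change, with no 0.15% margin and no named covariates.

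**The concern.** The same 80% is attached to two different effect sizes. With SD, sample size and alpha fixed, only one can be right. The Overview's version concerns the value that the hypothesis names and that the cited evidence supports, so it is the version a reader will carry away.

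Two misreadings could follow. After a non-significant result, a reader who believes the trial had 80% power for 0.15% may treat that effect as ruled out more firmly than the design allows. After a significant result, the wording of the hypothesis invites the conclusion that the effect is at least 0.15%, which a test against zero does not establish.

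**Working it through.** **Inputs.** SD of change 0.35% (Section 12, Table 5); 142 evaluable, so 71 per arm under 1:1 allocation (Sections 12 and 7.B); two-sided alpha 0.05 and unpaired t-test (Section 12, above Table 5); preliminary SD 0.28% (Section 12); disputed difference 0.15% (Overview).

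**Standard error of the difference in mean change.** SE = SD × √(2/71) = 2 × SD/√142.
- SD 0.35: 0.70/11.916 = 0.0587
- SD 0.28: 0.56/11.916 = 0.0470

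**Step 1: reproduce the plan's figure.** Detectable difference at 80% power = (1.960 + 0.842) × SE = 2.802 × 0.0587 = 0.165 by the normal approximation, and 0.166 by the noncentral t. Both round to the tabulated 0.17. Power at exactly 0.17 is 82.0% (t-test), so 0.17 is a rounded-up 0.166. Inflation for follow-up also reproduces: 142/0.95 = 149.5, or 150. The same method returns the Table 5 entries for glucose (5.9), insulin (3.3), HOMA-IR (0.95), SBP (2.0), DBP (1.4), total/HDL ratio (0.57), weight (3.1) and waist (3.8). Section 12 and Table 5 therefore agree with each other, and the Overview is the outlier.

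**Step 2: power for 0.15% at the planning SD.** Normal approximation: Φ(0.15/0.0587 − 1.960) = Φ(0.593) = 72.4%. By t-test:

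| Completers | SD 0.35 | SD 0.28 |
|---|---|---|
| 135 (90% follow-up) | 69.6% | 87.1% |
| 142 (95% follow-up) | 71.8% | 88.7% |
| 150 (no loss) | 74.1% | 90.3% |

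**Step 3: does any stated SD give 80% at 0.15%?** At SD 0.28 the detectable difference is 0.166 × 0.28/0.35 = 0.133%. The SD that gives 80% power at 0.15% with 142 completers is 0.15 × 0.35/0.1657 = 0.317%, which the protocol does not state. Neither documented SD reproduces the Overview.

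**Step 4: size needed for 80% at 0.15%, SD 0.35.** n per arm = 2 × 2.802² × 0.35²/0.15² = 85.5, so 86 per arm and 172 in total. The t-test gives 172.9, or 174 with equal arms. At 95% follow-up that is 172/0.95 = 181.1 (182 enrolled) or 174/0.95 = 183.2 (184 enrolled).

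**Step 5: what a significant or null result would show.** The smallest significant observed difference is 1.977 × 0.0587 = 0.116% at SD 0.35, or 1.977 × 0.0470 = 0.093% at SD 0.28. Both lie below 0.15%. At SD 0.35 the 95% confidence interval has half-width 0.116, so any observed difference between 0.15 − 0.116 = 0.034% and 0.116% would be non-significant while its interval still includes 0.15%.

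**The case against.** The strongest reply is that this is one summary sentence. Sections 12 and 13 govern sample size, test and alpha, none of them uses the Overview figure, and Section 12 states 80% for 0.17% openly. That is true, and it is why the remedy is confined to text. It does not make the sentence correct.

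Second, the true SD may be smaller than planned. With "the SD of the 6-month change in HbA1c is 0.28" per cent, power for 0.15% is about 89%, and the break-even SD of 0.317% lies about midway between the two documented values. This stands as a limit on the practical consequence: the real power may exceed 80%. The protocol nevertheless adopted 0.35%, and a power statement has to name the SD it rests on.

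Third, power might be recovered in other ways.
- Covariate adjustment would have to explain about 1 − (0.317/0.35)² = 18% of the variance of the change. Section 13.B.2 names no covariates and Section 12 assumes none.
- Averaging results from two laboratories is conditional on finding no systematic difference between them, and Section 12 takes no credit for it.
- A one-sided alpha of 0.05 would give 81.5% for 0.15%, but the protocol specifies a two-sided test.

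Fourth, Section 13.B.2 already frames the test as simple superiority, and the 0.15% in the hypothesis can be read as the expected effect. That reading is fair, and it supports bringing the Overview into line with Section 13.B.2. It is also fair that the protocol nowhere calls 0.15% the clinically relevant difference, although all the evidence it cites is scaled to that value. The misreadings described above are foreseeable rather than stated in the plan.

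**Conclusion.** The point holds. Under the protocol's planning assumptions (SD 0.35%, 142 completers split equally, two-sided alpha 0.05, unadjusted comparison of mean change), power for 0.15% is 71.8%, not 80%, and the chance of missing a true 0.15% effect is about 28%. The 80% figure belongs to 0.166%, reported as 0.17%. With follow-up between 90% and 100%, power for 0.15% at that SD runs from 69.6% to 74.1%. If the preliminary SD of 0.28% is the true one, power is 88.7%. The Overview figure therefore matches neither SD in the document. The hypothesis wording is a smaller, related mismatch: the planned test addresses any difference, not one of at least 0.15%.

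**What to change.** Replace the Overview power sentence with, for example:

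> *With 142 completers and an SD of change of 0.35%, power (two-sided alpha 0.05) is 80% for a difference of about 0.17% and about 72% for 0.15%. At the preliminary SD of 0.28%, power for 0.15% is about 89%.*

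Add the two 0.15% figures to Section 12 so that it agrees with the Overview. Table 5 is correct on HbA1c and needs no new number.

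Reword the primary hypothesis as superiority (a difference greater than zero), matching Section 13.B.2, and say that the 95% confidence interval will be read against 0.15% as the benchmark.

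The cost is text only: no added enrolment and no change to the test or the intervention. The one concession is a less favourable power figure at the planning SD. If the sponsor wants to keep 80% for 0.15%, it must either justify an SD of about 0.317% or less, or plan for about 174 completers at SD 0.35%.
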